|                              |   |
|------------------------------|---|
| Official Title:       | Moving PD-1 Blockade with Pembrolizumab into Concurrent Chemoradiation for Locally Advanced Non-Small Cell Lung Cancer (Multi-Center) |
| NCT number:           | NCT02621398   |
| Document Type:        | Study Protocol and Statistical Analysis study protocol SAP 2  |
| Date of the Document: | 10/21/21  |

- 3 Pathology report confirming diagnosis of NSCLC must be obtained and reviewed by the treating physician before registration to the study
- 4 Mandatory submission of unstained slides from an archived tumor block for PD-L1 analysis. Sites must verify that an archived tumor block is available before registration on the trial. Specimen can be obtained 70 days before initiation of chemoradiation treatment.
- 5 For women of childbearing potential only. This must be completed and negative within 7 days of registration for protocol therapy.
- 6 Correlative blood samples during radiation therapy on weeks 1, 3, 6 for CD8+ T cells and Tregulatory cells.
- 7 First Chest CT scan should be day 15 after the end of chemoradiation +/- 2 weeks. Following assessment with CT Chest every 9 weeks +/- 2 weeks during pembrolizumab therapy.
- 8 For patients starting pembrolizumab 2 weeks before end of CRT or at the start of CRT.
- 9 Correlative samples will be taken during cycles 1, 2, 3 of pembrolizumab
- 10 Thyroid screening will occur during day 22+7 days of chemoradiation when subject receives pembrolizumab concurrent with chemoradiation.
- 11 Every 12 weeks +14 days for the first year and every 16 weeks  $\pm$  14 days for the second year after treatment completes and every 6 months for years 3-5 and yearly thereafter. PET-CT may be done in place of regular CT at the discretion of the treating investigator.
- 12 Serious events and events of clinical interest will be collected for 90 days after the end of treatment with pembrolizumab
- 13 Treatment-related adverse events will be followed until resolution, return to baseline, or deemed clinically insignificant. Assessment of AEs includes events of clinical interest and immune related adverse events.
- 14 May be done within 3 days of chemotherapy.

[REDACTED] IRB  
IRB ID: [REDACTED]  
Approval Date: [REDACTED]  
Expiration Date: [REDACTED]

## 7.0 TRIAL PROCEDURES

### 7.1 Trial Procedures

The Trial Flow Chart - Section 6.0 summarizes the trial procedures to be performed at each visit. Individual trial procedures are described in detail below. It may be necessary to perform these procedures at unscheduled time points if deemed clinically necessary by the investigator.

Furthermore, additional evaluations/testing may be deemed necessary by the Sponsor and/or Merck for reasons related to subject safety. In some cases, such evaluation/testing may be potentially sensitive in nature (e.g., HIV, Hepatitis C, etc.), and thus local regulations may require that additional informed consent be obtained from the subject. In these cases, such evaluations/testing will be performed in accordance with those regulations.

#### 7.1.1 Administrative Procedures

##### 7.1.1.1 Informed Consent

The Investigator must obtain documented consent from each potential subject prior to participating in a clinical trial.

###### 7.1.1.1.1 General Informed Consent

Consent must be documented by the subject's dated signature or by the subject's legally acceptable representative's dated signature on a consent form along with the dated signature of the person conducting the consent discussion.

A copy of the signed and dated consent form should be given to the subject before participation in the trial.

The initial informed consent form, any subsequent revised written informed consent form and any written information provided to the subject must receive the IRB/ERC's approval/favorable opinion in advance of use. The subject or his/her legally acceptable representative should be informed in a timely manner if new information becomes available that may be relevant to the subject's willingness to continue participation in the trial. The communication of this information will be provided and documented via a revised consent form or addendum to the original consent form that captures the subject's dated signature or by the subject's legally acceptable representative's dated signature.

Specifics about a trial and the trial population will be added to the consent form template at the protocol level.

The informed consent will adhere to IRB/ERC requirements, applicable laws and regulations and Sponsor requirements.

### **7.1.1.2 Inclusion/Exclusion Criteria**

All inclusion and exclusion criteria will be reviewed by the investigator or qualified designee to ensure that the subject qualifies for the trial.

### **7.1.1.3 Medical History**

A medical history will be obtained by the investigator or qualified designee. Medical history will include all active conditions, and any condition diagnosed within the prior 10 years that are considered to be clinically significant by the Investigator. Details regarding the disease for which the subject has enrolled in this study will be recorded separately and not listed as medical history.

### **7.1.1.4 Prior and Concomitant Medications Review**

#### **7.1.1.4.1 Prior Medications**

The investigator or qualified designee will review prior medication use, including any protocol-specified washout requirement, and record prior medication taken by the subject within 28 days before starting the trial. Treatment for the disease for which the subject has enrolled in this study will be recorded separately and not listed as a prior medication.

#### **7.1.1.4.2 Concomitant Medications**

The investigator or qualified designee will record medication, if any, taken by the subject during the trial. All medications related to reportable SAEs and ECIs should be recorded as defined in Section 7.2.

### **7.1.1.5 Disease Details and Treatments**

#### **7.1.1.5.1 Disease Details**

The investigator or qualified designee will obtain prior and current details regarding disease status.

#### **7.1.1.5.2 Prior Treatment Details**

The investigator or qualified designee will review all prior cancer treatments including systemic treatments, radiation and surgeries.

#### **7.1.1.5.3 Subsequent Anti-Cancer Therapy Status**

The investigator or qualified designee will review all new anti-neoplastic therapy initiated after the last dose of trial treatment. If a subject initiates a new anti-cancer therapy within 30 days

after the last dose of trial treatment, the 30 day Safety Follow-up visit must occur before the first dose of the new therapy. Once new anti-cancer therapy has been initiated the subject will move into survival follow-up.

#### 7.1.1.6 Assignment of Subject Study Identification Number

A copy of the institution's IRB-approved informed consent document and written justification for any changes made to the informed consent for this protocol will be on file at [REDACTED] before [REDACTED]

Sites will contact the [REDACTED] OHRs Registration Desk ([REDACTED]) to register subjects. Registration/Enrollment process:

- Registration: Any subject that has signed the consent will be assigned a unique patient study number. Site will contact OHRs and send a copy of the de-identified consent. OHRs will provide site with the subject study number. The patient will not be identified by name.
- Enrollment: Once eligibility has been confirmed, the completed, signed and dated eligibility checklist will be sent to OHRs with additional source documents, if requested. OHRs Registration Desk will enroll the subject to the study and send a confirmatory email to the site. This is the point that the patient is considered on study.

- **Patients will not start protocol treatment prior to enrollment.**

#### 7.1.1.7 Trial Compliance (Medication/Diet/Activity/Other)

Interruptions from the treatment plan for >12 weeks between pembrolizumab doses require consultation between the investigator and Sponsor and written documentation of the collaborative decision on the management of the subject.

Administration of the pembrolizumab will be witnessed by the investigator and/or trial staff. The total volume of pembrolizumab infused will be compared to the total volume prepared to determine compliance to each dose administered.

## 7.1.2 Clinical Procedures/Assessments

### 7.1.2.1 Adverse Event (AE) Monitoring

The investigator or qualified designee will assess each subject to evaluate for potential new or worsening AEs as specified in the Trial Flow Chart and more frequently if clinically indicated. Adverse experiences will be graded and recorded throughout the study and during the follow-up period according to NCI CTCAE Version 4.0 (see Section 11.2). Toxicities will be characterized in terms regarding seriousness, causality, toxicity grading, and action taken with regard to trial treatment.

For subjects receiving treatment with pembrolizumab all AEs of unknown etiology associated with pembrolizumab exposure should be evaluated to determine if it is possibly an event of clinical interest (ECI) of a potentially immunologic etiology (termed immune-related adverse events, or irAEs); see the separate ECI guidance document regarding the identification, evaluation and management of potential irAEs.

Please refer to section 7.2 for detailed information regarding the assessment and recording of AEs.

### 7.1.2.2 Full Physical Exam

The investigator or qualified designee will perform a complete physical exam during the screening period. Clinically significant abnormal findings should be recorded as medical history. A full physical exam should be performed during screening.

### 7.1.2.3 Directed Physical Exam

For cycles that do not require a full physical exam per the Trial Flow Chart, the investigator or qualified designee will perform a directed physical exam as clinically indicated prior to trial treatment administration.

### 7.1.2.4 Vital Signs

The investigator or qualified designee will take vital signs at screening, prior to the administration of each dose of trial treatment and at treatment discontinuation as specified in the Trial Flow Chart (Section 6.0). Vital signs should include temperature, pulse, respiratory rate, pulse oximetry both walking and resting, weight and blood pressure. Height will be measured at screening only.

### 7.1.2.5 Eastern Cooperative Oncology Group (ECOG) Performance Scale

The investigator or qualified designee will assess ECOG status (see Section 11.1) at screening, prior to the administration of each dose of trial treatment and discontinuation of trial treatment as specified in the Trial Flow Chart.

### 7.1.2.6 Tumor Imaging and Assessment of Disease

Response assessments will be made both using the Immune Related Response Criteria, and using RECIST v1.1, allowing additional comparisons among these criteria for disease response assessment. The same measurable and non-measurable lesions will be followed by both RECIST v1.1 & irRC. RECIST 1.1 will be used to determine the primary objective of the trial and RECIST 1.1 and Immune Related Response Criteria will be used in secondary objective of PFS.

#### 7.1.2.6.1 Immune Related Response Criteria:

This study will use the Immune Related Response Criteria (irRC). These response criteria were developed to overcome the variable and unusual patterns of response to immunotherapeutic agents, in particular, ipilimumab [24]. The development of the guidelines were prompted by observations, mostly in patients with metastatic melanoma, of initial disease progression followed by later response, late responses, and mixed responses with an overall decrease in tumor burden.

#### 7.1.2.6.2 Antitumor response based on total measurable tumor burden

For the irRC, only index and measurable new lesions are taken into account (in contrast to conventional WHO criteria, which do not require the measurement of new lesions, nor do they include new lesion measurements in the characterization of evolving tumor burden). At the baseline tumor assessment, the sum of the products of the two largest perpendicular diameters (SPD) of all index lesions (five lesions per organ, up to 10 visceral lesions) is calculated. At each subsequent tumor assessment, the SPD of the index lesions and of new, measurable lesions (up to 5 new lesions per organ; 10 visceral lesions) are added together to provide the total tumor burden: Tumor Burden = SPDindex lesions + SPDnew, measurable lesions.

Table 7: Comparison between WHO criteria and the irRC criteria

|   | WHO   | irRC  |
|---|---|---|
| New, measurable lesions (ie $\geq 5 \times 5$ mm) | Always represent PD   | Incorporated into tumor burden  |
| New, nonmeasurable lesions (ie $< 5 \times 5$ mm) | Always represent PD   | Do not define progression (but preclude irCR)   |
| Non-index lesions                                 | Changes contribute to defining BOR of CR, PR, SD, and PD                              | Contribute to defining irCR (complete disappearance required)                         |
| CR  | Disappearance of all lesions in two consecutive observations not less than 4 wk apart | Disappearance of all lesions in two consecutive observations not less than 4 wk apart |
| PR  | $\geq 50\%$ decrease in SPD of all index lesions compared with                        | $\geq 50\%$ decrease in tumor burden compared with                                    |

|    |  |  |
|----|--|--|
|    | baseline in two observations at least 4 wk apart, in absence of new lesions or unequivocal progression of non-index lesions  | baseline in two observations at least 4 wk apart   |
| SD | 50% decrease in SPD compared with baseline cannot be established nor 25% increase compared with nadir, in absence of new lesions or unequivocal progression of non-index lesions | 50% decrease in tumor burden compared with baseline cannot be established nor 25% increase compared with nadir                           |
| PD | At least 25% increase in SPD compared with nadir and/or unequivocal progression of non-index lesions and/or appearance of new lesions (at any single time point)                 | At least 25% increase in tumor burden compared with nadir (at any single time point) in two consecutive observations at least 4 wk apart |

**7.1.2.6.3 Time-point response assessment using irRC**

Percentage changes in tumor burden per assessment time point describe the size and growth kinetics of both conventional and new, measurable lesions as they appear. At each tumor assessment, the response in index and new, measurable lesions is defined based on the change in tumor burden (after ruling out irPD). Decreases in tumor burden must be assessed relative to baseline measurements (i.e., the SPD of all index lesions at screening). The irRC were derived from WHO criteria and, therefore, the thresholds of response remain the same. However, the irRC response categories have been modified from those of WHO criteria as detailed.

[figure not shown]
**7.1.2.6.4 Overall response using the irRC**

The sum of the products of diameters at tumor assessment using the immune-related response criteria (irRC) for progressive disease incorporates the contribution of new measurable lesions. Each net Percentage Change in Tumor Burden per assessment using irRC criteria accounts for the size and growth kinetics of both old and new lesions as they appear.

Definition of Index Lesions Response Using irRC

- **irComplete Response (irCR):** Complete disappearance of all *index* lesions. This category encompasses exactly the same subjects as “CR” by the mWHO criteria

- **irPartial Response (irPR):** Decrease, relative to baseline, of 50% or greater in the sum of the products of the two largest perpendicular diameters of all *index* and all new measurable lesions (i.e., Percentage Change in Tumor Burden). Note: the appearance of new measurable lesions is factored into the overall tumor burden, but does not automatically qualify as progressive disease until the SPD increases by  $\geq 25\%$  when compared to SPD at nadir.
- **irStable Disease (irSD):** Does not meet criteria for irCR or irPR, in the absence of progressive disease.
- **irProgressive Disease (irPD):** At least 25% increase Percentage Change in Tumor Burden (i.e., taking sum of the products of all *index* lesions and any new lesions) when compared to SPD at nadir.

Definition of Non-Index Lesions Response Using irRC

- **irComplete Response (irCR):** Complete disappearance of all *non-index* lesions. This category encompasses exactly the same subjects as “CR” by the mWHO criteria.
- **irPartial Response (irPR) or irStable Disease (irSD):** *non-index* lesion(s) are not considered in the definition of PR, these terms do not apply.
- **irProgressive Disease (irPD):** Increases in number or size of *non-index* lesion(s) does not constitute progressive disease unless/until the Percentage Change in Tumor Burden increases by 25% (i.e., the SPD at nadir of the index lesions increases by the required amount).

Impact of New Lesions on irRC

New lesions in and by themselves do not qualify as progressive disease. However their contribution to total tumor burden is included in the SPD which in turn feeds into the irRC criteria for tumor response. Therefore, new non-measurable lesions will not discontinue any subject from the study.

**7.1.2.6.5 Definition of Overall Response Using irRC**

Overall response using irRC will be based on these criteria (see Table 9):

- **Immune-Related Complete Response (irCR):** Complete disappearance of *all* tumor lesions (index and nonindex together with no new measurable/unmeasurable lesions) for at least 4 weeks from the date of documentation of complete response.
- **Immune-Related Partial Response (irPR):** The sum of the products of the two largest perpendicular diameters of all index lesions is measured and captured as the SPD baseline. At each subsequent tumor assessment, the sum of the products of the two largest perpendicular diameters of all index lesions and of new measurable lesions are added together to provide the Immune Response Sum of Product Diameters (irSPD). A decrease, relative to baseline of the irSPD compared to the previous SPD baseline, of 50% or greater is considered an immune Partial Response

[REDACTED] IRB  
IRB ID: [REDACTED]  
Approval Date:  
Expiration Date:

(irPR).

- **Immune-Related Stable Disease (irSD):** irSD is defined as the failure to meet criteria for immune complete response or immune partial response, in the absence of progressive disease.
- **Immune-Related Progressive Disease (irPD):** It is recommended in difficult cases to confirm PD by serial imaging. Any of the following will constitute progressive disease:
  - At least 25% increase in the sum of the products of all index lesions over nadir SPD calculated for the index lesions.
  - At least a 25% increase in the sum of the products of all index lesions and new measurable lesions (irSPD) over the baseline SPD calculated for the index lesions.

Immune-Related Best Overall Response Using irRC (irBOR)

irBOR is the best confirmed irRC overall response over the study as a whole, recorded between the date of first dose until the last tumor assessment before subsequent therapy (except for local palliative radiotherapy for painful bone lesions) for the individual subject in the study. For the assessment of irBOR, all available assessments per subject are considered. irCR or irPR determinations included in the irBOR assessment must be confirmed by a second (confirmatory) evaluation meeting the criteria for response and performed no less than 4 weeks after the criteria for response are first met.

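### Section 7.1.2.6.5 defines immune-related progression differently from the rest of the irRC text, so the same scans can give different irRC categories or irRC PFS dates

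*Combined protocol and SAP*

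**What the plan says.** Section 7.1.2.6 names irRC, with RECIST 1.1, as a criterion for secondary PFS. The irPD rule then appears in several places.

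- **Table 7 (7.1.2.6.2), irRC column:** "At least 25% increase in tumor burden compared with nadir (at any single time point) in two consecutive observations at least 4 wk apart". Tumour burden in that section is index plus new measurable lesions.
- **Section 7.1.2.6.4:** irPD is a rise of at least 25%, counting index "lesions and any new lesions) when compared to SPD at nadir". No confirmation is stated here. The section adds that "New lesions in and by themselves do not qualify as progressive disease".
- **Table 8 footnote:** irPD is taken to be confirmed at a further assessment four or more weeks on. The table gives the 25% threshold but does not name nadir.
- **Section 7.1.2.6.5:** either of two conditions is enough. The first is "At least 25% increase in the sum of the products of all index lesions over nadir SPD calculated for the index lesions". The second is "At least a 25% increase in the sum of the products of all index lesions and new measurable lesions (irSPD) over the baseline SPD" of the index lesions. On confirmation it says only: "It is recommended in difficult cases to confirm PD by serial imaging".

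Section 7.1.2.6.5 refers the reader to Table 9, which is the RECIST target-lesion table; the irRC derivation is Table 8. The PFS definition in Section 8.2 names no irPD rule and does not say which scan dates the event.

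**The concern.** The second condition in 7.1.2.6.5 uses a different reference value from Table 7 and 7.1.2.6.4, and its confirmation sentence is weaker than Table 7 and the Table 8 footnote. Nothing in the published text says which statement governs. Two assessors following different paragraphs could therefore record different results from identical measurements.

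The time-point category is exposed as well as the PFS date. Section 7.1.2.6.3 says response in index and new measurable lesions "is defined based on the change in tumor burden (after ruling out irPD"), so the irPD reference decides whether a scan can be called irPR or irSD at all.

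Section 8.2 plans Kaplan-Meier estimates and one-sample log-rank comparisons with historical controls for PFS. Both depend on event counts and event times, and the trial is small.

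**Working it through.** The plan states no figure to reproduce. The check applies each rule as written to the same scans.

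**Threshold algebra.** Baseline is the screening value (Section 7.1.2.6.3: "baseline measurements (i.e., the SPD of all index lesions at screening"). Set baseline SPD = 1. Let r be the fractional fall to nadir and g the index regrowth over nadir, with 0 ≤ g < 0.25. Assume new lesions appear after nadir. Then nadir = 1 − r and current index SPD = (1 + g)(1 − r).

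- Nadir rule: (1 + g)(1 − r) + new ≥ 1.25(1 − r), so new ≥ (0.25 − g)(1 − r).
- Section 7.1.2.6.5, second condition: (1 + g)(1 − r) + new ≥ 1.25, so new ≥ 0.25 + r − g(1 − r).
- Difference: 1.25r, whatever g is.

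New-lesion area needed, as a fraction of baseline SPD, with g = 0:

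| r | Nadir rule | 7.1.2.6.5 | Gap |
|---|---|---|---|
| 0 | 0.25 | 0.25 | 0 |
| 0.2 | 0.20 | 0.45 | 0.25 |
| 0.5 | 0.125 | 0.75 | 0.625 |
| 0.7 | 0.075 | 0.95 | 0.875 |

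At r = 0.5 and g = 0.1 the pair is 0.075 and 0.70, again a gap of 0.625. The conflict vanishes at r = 0. It also vanishes at g ≥ 0.25, because the first condition of 7.1.2.6.5 then calls irPD against nadir too.

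**Category example (sizes assumed).** Baseline 1000, nadir 300, then index 300 plus new lesions 120 = 420. Against nadir, 420/300 = +40%, which meets the irPD threshold subject to confirmation. Against baseline, 420/1000 = −58%, which meets the irPR threshold, and 7.1.2.6.5 does not call irPD.

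**Date examples (sizes assumed, baseline 2500 mm²).** Chemoradiation ends at day 42 (Section 8.1). The first CT is 15 days later, at day 57 or about week 8. Nine-weekly scans (flow chart footnote 7) then fall at about weeks 17, 26, 35 and 44.

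- *7.1.2.6.5 later, r = 0.5.* Index stays at 1250 from week 8, and a new lesion measures 20×20, 30×30, 40×40 and 50×50 mm from week 17. Totals are 1650, 2150, 2850 and 3750. Against nadir: +32% at week 17, confirmed at week 26 (+72%). Against baseline: −34%, −14%, +14%, +50%, so 7.1.2.6.5 is first met at week 44. The gap is 44 − 17 = 27 weeks.
- *7.1.2.6.5 later, r = 0.2.* Index 2000, new lesion 25×25, 30×30 and 35×35 mm. Totals are 2625, 2900 and 3225. Against nadir: +31% at week 17, confirmed at week 26 (+45%). Against baseline: +5%, +16%, +29%, so 7.1.2.6.5 is met at week 35. The gap is 18 weeks.
- *7.1.2.6.5 earlier.* Index 2000, 2550, 2200, 2100 at weeks 8 to 35, with no new lesion. At week 17, 2550/2000 = +27.5%, so 7.1.2.6.5 can record irPD. At week 26, 2200/2000 = +10%, so Table 7 records no event.
- *Agreement.* No shrinkage, new lesion area 700 then 1000 mm². 3200/2500 = +28% and 3500/2500 = +40%. Both rules are met at week 17 if the event is dated at the first scan.

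**Weight of one patient.** 1/14 = 7.1%, 1/19 = 5.3%, 1/42 = 2.4%. These are crude proportions, not Kaplan-Meier estimates.

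**The case against.** The best defence is that the protocol as a whole expects confirmed progression. Tables 7 and 8 say so, Section 7.1.5.4.1 moves patients to survival follow-up on confirmed progression, and Section 7.1.5.5 requires it for retreatment. The softer sentence in 7.1.2.6.5 could be read as a stray, and an unsustained rise is arguably the kind of hard case where it advises repeat imaging. This weakens the confirmation half. It does not remove it, because a recommendation still allows an unconfirmed event to be recorded, and it leaves the baseline-versus-nadir conflict untouched.

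A reader might infer from the examples that irRC PFS will be wrong by 18 to 27 weeks. The documents do not support that. Shrinkage, regrowth and lesion sizes are all assumed. The new lesion at week 17 is already RECIST progression (Table 11), so imaging might not continue to week 35 or 44. Read literally, the general PFS wording in 8.2 would also date progression at week 17; but 7.1.2.6 separately names irRC for PFS, so the irRC version still needs one rule.

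A reader might also infer a bias in a known direction. The baseline reference delays irPD and optional confirmation can bring it forward, so the net direction is unknown. Nor is a new lesion irPD by its mere appearance under any of these rules.

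Finally, this is a 3+3 safety trial and PFS is also assessed by RECIST 1.1. That is fair and limits the weight of the point.

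**Conclusion.** The conflict is real and lies in the current text. Section 7.1.2.6.5 is the outlier: Table 7 and 7.1.2.6.4 use nadir for index plus new lesions, and Table 7 and the Table 8 footnote require confirmation. The reference conflict applies only after shrinkage, with index regrowth below 25% over nadir and new measurable lesions; there the gap is exactly 1.25r of baseline SPD. The confirmation conflict applies to rises that are not sustained.

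The algebra needs no trial data. How many patients would be affected, and by how many weeks, cannot be derived from the documents. The consequence is confined to irRC response and irRC PFS. Extending it to the dose-finding result or RECIST PFS would go beyond the text, since neither uses the irPD rule. It should be corrected before analysis, as a wording inconsistency in the event rule of a named secondary endpoint.

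**What to change.** In 7.1.2.6.5, replace both irPD conditions and the sentence on confirmation with the Table 7 rule: irSPD (index plus new measurable lesions) at least 25% above nadir, confirmed at the next consecutive assessment, no sooner than 4 weeks later. Point the section to Table 8 instead of Table 9. Leave RECIST PFS as it is.

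As an accompanying clarification only, Section 8.2 could state which of the two scans dates the irRC PFS event (on the nine-week schedule the choice moves it by about 9 weeks) and how patients with no confirming scan are handled, with their number reported. Any reasonable convention will do if it is fixed before analysis.

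The cost is a few sentences. For disease seen on chest CT during pembrolizumab no extra scan is needed: with nine-weekly CT and a window of ±2 weeks, consecutive scans are at least 9 − 2 − 2 = 5 weeks apart, above the 4-week minimum. The small downside is that irPD cannot be confirmed where no later scan exists, so those patients depend on the stated convention.
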